8.3.1.2. Additional Analyses of the Primary Efficacy Endpoint

The primary efficacy analysis will be repeated using the ITT population, ATP, and PP population. Analyses will be conducted with LOCF from Week 8 onward and repeated excluding missing data (no LOCF).

In addition to the primary analysis of Week 12 that includes all subjects who had no more than 12 weeks of study treatment, an analysis of the End of Treatment MRI-PDFF data including data from the extended dosing subjects will be performed in the mITT, ITT, ATP, and PP populations.

An analysis of MRI-PDFF data in the log scale will be performed in the mITT population. The log ratio of Week 12 to baseline [$\log(\text{Week 12}/\text{Baseline})$] will be analyzed using a similar

ANCOVA mode. In the event that model assumptions are not met for the primary efficacy analysis noted above, the analysis in the log scale will become primary.

At the time of the final analysis, the above analyses will be repeated using all data from the US and China. Subset analyses will be performed on the primary efficacy endpoints for subjects enrolled in US and China to evaluate the consistency of results between subjects enrolled in each country. The ANCOVA model will incorporate fixed effects for the stratification factor (diabetes presence/absence), country (US/China), treatment group (TVB-2640 50 mg and pooled placebo), and country-by-treatment interaction and with the baseline MRI-PDFF value as a covariate including all subjects in the mITT from US and China who received 50 mg or placebo.

A test for country-by-treatment interaction will be performed. If there is no interaction detected ($p \geq 0.05$), the primary efficacy endpoint, percent change from baseline in hepatic fat fraction at Week 12, as determined by MRI PDFF, will be analyzed using an ANCOVA model with fixed effects for the stratification factor (diabetes presence/absence) and treatment group (i.e., TVB-2640 dose groups and pooled placebo) and with the baseline MRI-PDFF value as a covariate including all subjects from US and China (with no fixed effect for country). If the country-by-treatment interaction is significant ($p < 0.05$) then a separate analysis will be performed on subjects enrolled in China in the 50 mg cohort. This analysis is not powered to detect a significant difference but would be supportive/descriptive in nature to evaluate trends.

Analyses of absolute reduction from baseline to week 12 in liver fat will be performed in the mITT, ITT, ATP, and PP populations. Similar methodology as used for the primary efficacy analysis will be used.

In order to determine if the effect on liver fat persists after study treatment, the absolute and percent change in liver fat from End of Treatment to End of Study will be performed in the mITT population with missing data excluded. The analysis will be run with and without dosing extenders. Methodology similar to that described for the primary efficacy analysis will be used.

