In Cohorts 1 and 2, subjects will undergo MRI-PDFF prior to the start of treatment (pre-dose), at the end of the initial 12-week Treatment Period (between 11 and 12 weeks after the start of treatment), and at Week 16. Due to the COVID-19 pandemic, if the subject is unable to attend the Week 12 visit, one MRI-PDFF may be performed at any time between Week 11 and 16. If this scan is performed after Week 12, the subject must continue to receive study drug until the final scan is performed. However, study drug is not to be continued for >16 weeks. In Cohort 3, MRI-PDFF will undergo MRI-PDFF prior to the start of treatment (pre-dose) and at the end of the initial 12 week Treatment Period (between 11 and 12 weeks after the start of treatment).

During the study, safety will be assessed by vital signs (oral temperature, pulse, respiratory rate, and seated blood pressure), 12-lead ECG, physical examination, including ophthalmologic examination, and clinical laboratory testing (hematology, chemistry, and urinalysis). Subjects will be evaluated for AEs and concomitant medication use throughout the study.

Blood samples will be collected at specified times for the assessment of PK.

An SRC will oversee the study to ensure subject safety and to advise if any dosing alterations are recommended. The SRC will review safety including liver-related events (i.e., clinically meaningful elevations in ALT, AST, and bilirubin), and other efficacy (lipid parameters) and safety data as needed.

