8.9. Subject Adherence to Protocol Schedule

All subjects are required to adhere to the protocol-specified visit schedule.

Subjects will be evaluated for study eligibility during the screening period, within 60 days before randomization. All subjects must provide written informed consent before any study-related samples are collected or evaluations performed in this study.

Subjects who are determined to be eligible for the study will be randomized within 24 hours before baseline (Day 1, the first day of study drug administration). Thereafter, subjects are to attend study center visits at Day 2 and Week 2, 4, 8, and 12. Subjects who discontinue study drug before completion of the Week 12 visit are to attend an Early Termination visit within 1 week after the last study drug dose. All study visits are to be conducted on an out-patient basis. Additional study center visits may be scheduled, as deemed necessary based on the subject's clinical status.

Permissible visit windows are specified in [Table 2](#).

A Follow-up visit will be conducted at Week 16 (± 1 week) for MRI-PDFF, measurement of liver aminotransferases, and safety assessments. Additional safety follow-up may be required thereafter if drug-related AEs have not resolved at that time.

Failure to attend scheduled study visits within the protocol-specified windows may result in discontinuation from the study.

The Sponsor notes that the COVID-19 pandemic may impact the conduct of the 50 mg and 75 mg cohorts, with challenges potentially arising from quarantines and travel limitations affecting study subjects as well as clinic and imaging facility closures. Accordingly, safety assessments scheduled for the Week 12 and 16 visits, as identified in [Table 2](#), including sample

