5. ANALYSIS POPULATIONS/SETS

The modified intent-to-treat population (mITT) is defined as all subjects who are randomized, receive study drug for at least 8 weeks, and have a baseline and at least 1 post-baseline MRI-PDFF assessment on or after Week 8. The mITT is the primary population for analysis of MRI-PDFF assessments and subjects will be analyzed according to the randomized treatment assignment.

The intent-to-treat population (ITT) is defined as all subjects who are randomized and received at least 1 dose of study drug. The ITT will be used for analysis of a subset of secondary efficacy endpoints and supportive and sensitivity analyses of MRI-PDFF assessments. Subjects will be analyzed according to the randomized treatment assignment.

The as-treated population (ATP) is defined as all subjects who are randomized and received at least 1 dose of study drug. The ATP will be used for analysis of secondary efficacy endpoints and supportive and sensitivity analyses of MRI-PDFF assessments. Subjects will be analyzed according to the treatment received.

The safety population is defined as all subjects who are randomized and received at least 1 dose of study drug and will be used for all analysis of safety. Subjects will be analyzed according to

the treatment received. If all subjects were dosed according to randomized treatment assignment, then the safety population and ITT are identical.

A per-protocol (PP) population may be defined for sensitivity analyses of the efficacy endpoints. The PP population will be based on subjects in the mITT population with data excluded from subjects who have important protocol violations deemed to possibly affect the efficacy measurements or integrity of any other key study data. Subjects will be analyzed according to the actual treatment received. If a PP population is implemented, details on subjects excluded will be provided in the CSR.

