7.8. Missing Data

Imputation will only be performed on the primary and selected secondary efficacy endpoints using MRI-PDFF data.

In the primary and key secondary analyses, missing Week 12 values for MRI-PDFF will be imputed with the last post-baseline observation on or after Week 8. For sensitivity analyses that include subjects with extended dosing, the End of Treatment values for MRI-PDFF will be imputed with the last post-baseline observation on or after Week 8.

MRI-PDFF analyses at other timepoints (e.g., End of Study) will follow similar conventions and use the last-post baseline observation on or after Week 8. Missing MRI-PDFF data before Week 8 will not be imputed.

Sensitivity analyses will be performed excluding data from subjects with missing data (i.e., observed cases approach).

Additional details are provided in the relevant analysis sections below.

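### The Week 12 ITT and ATP repeats of the MRI-PDFF analyses cannot assess early drop-out, because almost no subject who stops before Week 8 receives a value in them

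*SAP*

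**What the plan says.** **Populations (SAP Section 5).** mITT subjects must "receive study drug for at least 8 weeks, and have a baseline and at least 1 post-baseline MRI-PDFF assessment on or after Week 8". ITT and ATP need no scan; each "is defined as all subjects who are randomized and received at least 1 dose of study drug".

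**Week 12 repeats (SAP 8.3.1.2, 8.3.2).** The primary analysis is repeated in ITT, ATP and PP, and the responder analysis likewise. On missing values: "Analyses will be conducted with LOCF from Week 8 onward and repeated excluding missing data (no LOCF".

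**Missing data (SAP 7.8).** "Missing MRI-PDFF data before Week 8 will not be imputed". The other approach is: "Sensitivity analyses will be performed excluding data from subjects with missing data (i.e., observed cases approach". By default, percentages use non-missing values only (SAP Section 7).

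**Scans (Protocol 7.1, 8.9, Table 2).** In Cohorts 1 and 2, "subjects will undergo MRI-PDFF prior to the start of treatment (pre-dose), at the end of the initial 12-week Treatment Period" and at Week 16. Table 2 adds a scan at Early Termination. Subjects who stop before completing Week 12 "are to attend an Early Termination visit within 1 week after the last study drug dose".

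**End of Treatment (SAP 3.1, 8.3.1.2).** A further analysis in mITT, ITT, ATP and PP uses the End of Treatment scan. For a subject with under 12 weeks of drug, that visit is one before Week 12, with no lower limit at Week 8.

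**Commitment (Protocol 13.2.2).** The SAP was to describe sensitivity analyses using other missing-data methods and other populations.

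**The concern.** mITT is defined by what happens after randomisation, so the natural check on it is an analysis that brings back the subjects it leaves out. The Week 12 ITT and ATP repeats look like that check. Under their own missing-data rules, however, nearly all of those subjects drop out again for want of a value. A clinical study report could then present close agreement between mITT and ITT as robustness to early drop-out, when the two analyses used almost the same people.

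Informative loss is plausible. Protocol 8.6 ties permanent discontinuation to significant skin, eye and respiratory findings, and Protocol 5.1 names skin and ocular effects as the drug's main toxicities in oncology patients. Protocol 9.6 discontinues subjects at 25 mg who need a dose reduction. Apart from imaging staff, site personnel know the assignment (Protocol 9.9), so discretionary withdrawals are made with that knowledge.

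**Working it through.** **1. Who enters which analysis** (extended-dosing subjects set aside; the SAP handles them separately)

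| Dosed subject | mITT | Week 12 ITT/ATP, LOCF | Week 12 ITT/ATP, observed | End of Treatment ITT/ATP |
|---|---|---|---|---|
| At least 8 weeks of drug, scan from Week 8 on | in | in | in if scanned at Week 12 | in |
| Under 8 weeks, Early Termination scan on or after Week 8 | out | in | out (nominal visits, SAP 7.7) | in |
| Under 8 weeks, only scan before Week 8 | out | out | out | in, unless 7.8 bars it |
| No post-baseline scan | out | out | out | out |

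Only the second row separates the Week 12 ITT repeat from mITT.

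**2. How large is that row?** Assumptions: 5-25% of dosed subjects stop before Week 8, evenly over the 8 weeks, and the Early Termination scan is their last. With that visit within 1 week of the last dose, only stops in the final week before Week 8 can qualify, so at most 1/8 do.

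- Dosed N for 30 evaluable = 30/(1 − d), rounded up: 32 at 5%, 40 at 25%.
- Early stoppers per group: 2 to 10.
- Recovered per group, LOCF version: 2/8 = 0.25 to 10/8 = 1.25. Over three groups: 0.75 of 6 to 3.75 of 30.
- Recovered, observed-case version: about 0.

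**3. Responder illustration.** Assumed: 30 dosed per arm; 4 active and 1 placebo lost before Week 8 without a value; 5 placebo responders. Unstratified CMH, 1 df: χ² = (N − 1)(ad − bc)² / (n₁n₀m₁m₀), where a and b are active responders and non-responders, c and d the same for placebo, n the arm totals and m the outcome totals.

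- 11 responders, mITT: 54 × (11×24 − 15×5)² / (26×29×16×39) = 54 × 189² / 470,496 = 4.10.
- 11 responders, all dosed: 59 × (11×25 − 19×5)² / (30×30×16×44) = 59 × 180² / 633,600 = 3.02.

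| Active responders | mITT, active v placebo | χ² | p | Lost as non-responders | χ² | p |
|---|---|---|---|---|---|---|
| 10 | 38.5% v 17.2% | 3.06 | 0.080 | 33.3% v 16.7% | 2.19 | 0.139 |
| 11 | 42.3% v 17.2% | 4.10 | 0.043 | 36.7% v 16.7% | 3.02 | 0.082 |
| 12 | 46.2% v 17.2% | 5.27 | 0.022 | 40.0% v 16.7% | 3.96 | 0.047 |
| 14 | 53.8% v 17.2% | 7.98 | 0.005 | 46.7% v 16.7% | 6.13 | 0.013 |

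From 8 to 17 active responders, 11 is the only count at which significance at 0.05 changes.

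**4. Continuous illustration.** The plan's own power figures come first. Simulated Wilcoxon tests on lognormal data (SD 30, difference 24, placebo mean assumed to be 100% of baseline because none is given) yield 83.6% for both doses with 30 per group (stated: at least 80%) and 77.4% for 30 v 15 (stated: at least 77%). The normal approximation for one comparison is Φ(24 / (30√(2/30)) − 1.96) = Φ(1.14) = 87%.

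Now give every early stopper a mean change of zero, with SD still 30 and equal loss in each group. The difference becomes 24 × 30/N:

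| Early stops | N dosed | Difference | One-comparison power |
|---|---|---|---|
| 0% | 30 | 24.0 | 87% |
| 5% | 32 | 22.5 | 85% |
| 10% | 34 | 21.2 | 83% |
| 15% | 36 | 20.0 | 81% |
| 20% | 38 | 18.9 | 79% |
| 25% | 40 | 18.0 | 77% |

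**The case against.** The strongest reply is that the SAP does have an analysis that can use early scans. The End of Treatment analysis runs in ITT and ATP, its visit definition has no Week 8 floor, and SAP Section 7 includes all data up to withdrawal whatever the treatment duration. A reader might infer from the Week 12 rules that Early Termination scans are never used, or that no ITT analysis can bear on early drop-out. The documents do not support that: on a plain reading, an observed Week 5 scan enters. This stands, but the check is partial. It mixes treatment durations and omits anyone unscanned, and 7.8 leaves unclear whether its Week 8 limit covers only imputation or also bars observed earlier scans.

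SAP 8.3.2 also reports the key secondary endpoint in all ATP subjects and separately in the mITT-like subset, so it expects the two to differ. It does not say how an unscanned ATP subject counts, and the non-missing default would drop that subject. Observed cases is formally another missing-data method, so Protocol 13.2.2 is arguably met in the letter; it still gives no outcome to those without a scan.

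A reader might also infer that early loss will be frequent, drug-related and enough to overturn the result. No drop-out figure is given. Protocol 8.6 lets study drug be interrupted and resumed for mild to moderate PPE, although its lead-in reads more broadly and the two need reconciling. Protocol 9.6 allows dose reduction at 50 mg. The responder illustration assumes its imbalance, and 30 dosed per arm is a simplification: US enrolment aims for 30 evaluable active subjects per cohort. Finally, the 1-in-8 bound assumes no later scan. The SAP does not say whether subjects withdrawn early have an End of Study scan.

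**Conclusion.** The point holds for the Week 12 ITT and ATP repeats. By their own rules they rest on nearly the same subjects as mITT, so agreement with mITT says little about early drop-out. Under the even-stopping assumption they recover at most about 1 in 8 early stoppers with LOCF and about none without it. No planned MRI-PDFF analysis assigns an outcome to every dosed subject.

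The effect on conclusions is uncertain and probably modest. Under the assumed losses, a borderline responder result can lose significance and a clear one keeps it. For the continuous endpoint, a no-change assumption would shrink a difference of 24 to between 22.5 and 18.0 over 5-25% early stopping. The point concerns supportive analyses only; it does not show that the primary analysis is biased.

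**What to change.** 1. **Responder analyses in ITT and ATP (SAP 8.3.2).** Keep all dosed subjects in the denominator and count anyone with no post-baseline MRI-PDFF as a non-responder. For subjects whose only scan is an Early Termination scan before Week 8, state one rule and apply it consistently: either use the observed scan in the End of Treatment version, or count the subject as a non-responder in the Week 12 version. Leave the separate handling of extended-dosing subjects as it is.
2. **SAP 7.8.** State that observed Early Termination scans before Week 8 enter the ITT and ATP End of Treatment analysis, and that the Week 8 limit applies to imputation only.
3. **SAP 8.3.1.2.** Add one continuous ITT sensitivity analysis that gives unscanned subjects an outcome under a no-benefit assumption. Baseline carried forward and placebo-based imputation are both reasonable; the choice should be fixed in advance.

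The primary analysis, the testing sequence and data collection do not change. The cost is a few lines of SAP text, a little programming, and sensitivity estimates that will be somewhat less favourable.

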13.2.2. Efficacy Analysis

A test for country-by-treatment interaction with respect to the primary efficacy endpoint, percent change from baseline in hepatic fat fraction at Week 12, as determined by MRI-PDFP, will be performed in the 50 mg cohort. An ANCOVA model with fixed effects for the stratification factor (diabetes presence/absence), country (US/China), treatment group (TVB-2640 50 mg and pooled placebo), and country-by-treatment interaction and with the baseline MRI-PDFP value as a covariate including all subjects from US and China will be performed. If there is no interaction detected ($p \geq 0.05$), the primary efficacy endpoint, percent change from baseline in hepatic fat fraction at Week 12, as determined by MRI PDFP, will be analyzed using an analysis of covariance (ANCOVA) model with fixed effects for the stratification factor (diabetes presence/absence) and treatment group (i.e., randomized TVB-2640 dose groups and pooled placebo) and with the baseline MRI-PDFP value as a covariate including all subjects from US and China. If the country-by-treatment interaction is significant ($p < 0.05$) then the primary analysis will be conducted on subjects enrolled in the US and will maintain sufficient power with the 90 evaluable subjects in the US (30 active in each cohort and 30 combined placebo). A separate analysis would be performed on subjects enrolled in China in the 50 mg cohort. This analysis is not powered to detect a significant difference but would be supportive/descriptive in nature to evaluate trends.

The primary efficacy analyses will be based on a F-test from the ANCOVA model in the mITT to compare each randomized TVB-2640 dose group individually with the placebo group. The fixed-sequence method, as described below, will be used to maintain an overall 0.05 Type I error rate. Data normality will be assessed and the appropriate data transformation will be applied to fulfill the underlying assumption of the ANCOVA model; if a suitable transformation cannot be determined the corresponding rank ANCOVA will become the primary analysis for this endpoint. Treatment interaction will be evaluated among the treatment groups, and if needed it

will be considered supportive of the primary efficacy analyses. Summary statistics will be displayed by treatment group along with the difference in least squares means (and the associated 95% confidence interval and p-value) for each randomized TVB-2640 dose group to pooled placebo comparison.

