3.3. Sample Size Considerations

The sample size is based on a fixed-sequence strategy which tests for a treatment difference in the primary endpoint (percent change at Week 12 in liver fat from baseline as determined by

MRI-PDFF) between each TVB-2640 dose group versus placebo. The fixed-sequence strategy will start with the highest dose group comparison. If statistically significant, then testing will proceed to the low dose group comparison. Each TVB-2640 dose group will be compared to the pooled placebo group using an F-test test from an analysis of covariance (ANCOVA) model with fixed effects for the stratification factor (diabetes presence/absence) and treatment group (i.e., TVB-2640 dose groups and pooled placebo) and with the baseline MRI-PDFF value as a covariate. Since the primary efficacy endpoint may not be normally distributed, the non-parametric Wilcoxon rank-sum test is conservatively used, instead of the F-test, for power calculations.

The sample size is based on a conservative assumption that the primary analysis is going to be performed in the US population only, resulting in 30 evaluable subjects in the placebo group, and 30 evaluable subjects in each of the TVB-2640 dose levels. Based on Patel (2016), it is conservatively assumed that the primary endpoint has a standard deviation of 30. Power calculations assume the primary endpoint is lognormally distributed with a standard deviation of 30, there are at least 30 evaluable subjects in each treatment group, and the two-sided Wilcoxon rank sum test will be used to test each pairwise treatment difference at the 0.05 Type I error level. Under the fixed-sequence strategy which maintains an overall 0.05 Type I error rate, the study has at least 80% overall power to detect both treatment differences (i.e., both high dose versus placebo and low dose versus placebo), if each mean treatment difference is at least 24. If the study does not proceed to the high-dose level, (i.e., there are 30 evaluable subjects treated with 25 mg TVB-2640 and only 15 with placebo), then the study has at least 77% power to detect a mean treatment difference of at least 24. The study will have more power if the subjects from China are included in the primary analysis and the same assumptions of treatment difference and variability hold.

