3.5. Timing of Analyses

An interim analysis for SRC review will be performed after all of the subjects in the 25 mg dose level complete the 12-week treatment period. Details on data requirements and outputs required will be maintained in the SRC Plan or other related documents.

An additional SRC analysis was performed during the COVID pandemic to confirm safety prior to allowing the option for extended 50 mg cohort dosing.

The primary analysis of efficacy will be performed when all subjects in the US 50 mg cohort finish their final visit. The primary analysis will not include any data from China, due to delays and uncertainty of enrollment in the Chinese cohort.

An End of Study final analysis will be performed when the final subject completes the study and will include cumulative data from the US and China as applicable.

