6. DEFINITIONS

7. GENERAL DATA HANDLING CONSIDERATIONS

All analyses will be conducted using SAS® software Version 9.4 or higher.

All data in the database will be presented in by-subject data listings.

Unless otherwise stated, all listings will be sorted by treatment group, center ID, subject number, and assessment date and time, if available.

Unless stated otherwise, continuous data will be summarized by treatment group using descriptive statistics including number of subjects (n), mean, median, standard deviation (SD), first quartile (Q1), third quartile (Q3), minimum (min) value, and maximum (max) value.

Unless stated otherwise, categorical data will be summarized by treatment group using counts and percentage based on the number of non-missing values. For selected summaries, the number of missing values will be presented as a separate category with no percentage, if one or more subjects have missing data. Counts of zero will be presented without percentages.

Descriptive statistics will be presented with the following numerical precision:

- Minimum and Maximum: same as the raw data collected
- Mean, Median, Q1, and Q3: one additional decimal place to that reported for Minimum and Maximum
- SD: two additional decimal places than the Minimum and Maximum
- Percentages: reported to one decimal place if percent is <100. If the value is 100, no decimal place will be reported.

Unless otherwise noted, statistical inference will be based on 2-sided testing with a 5% significance level (i.e. 95% confidence intervals [CI] will be produced).

P-values will be reported to four decimal places. If the value is below 0.0001 it will be noted as < 0.0001; if the value above 0.9999 it will be noted as > 0.9999.

Sponsor: Sagimet Biosciences
Protocol Number: 3V2640-CLIN-005
Version and Date: Final Version 1, 02June2020

All data up to the time of study completion/withdrawal from the study will be included in the analysis, regardless of duration of treatment.

Numbering for data displays will be based on International Council for Harmonisation (ICH) E3 whenever possible.

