treatment group, visit, and treatment-by-visit interaction as the fixed effects, and baseline value as a covariate, and the model will use an unstructured variance-covariance matrix. The point estimates for the least-squares mean of the pairwise difference for each TVB-2640 dose group and pooled placebo comparison at each visit and the corresponding 95% confidence interval and two-sided p-value will be summarized. If convergence problems arise when fitting the model, a spatial power covariance structure will be used as a first step. If the model still has convergence issues, compound symmetry covariance structure will be employed.

For the end of study final analysis, if a country-by-treatment interaction is found in the primary efficacy endpoint, the subjects from the US and China in the 50 mg cohort will be analyzed separately. However, if no country-by-treatment interaction is found in the primary efficacy endpoint, the interaction may be explored within the secondary endpoints in a similar manner in order to determine if there is a significant interaction for any of the other endpoints (e.g., ALT or AST).

The model produces asymptotically consistent estimates when data are missing at random. No imputation of missing data will be required for these analyses. By definition, subjects without a baseline and at least 1 post-baseline value will be excluded from the MMRM analyses. Model assumptions (normality of residuals and parallel slopes) may be assessed. If assumptions are not met, then transformations will be done analogous to the primary efficacy analyses described above.

Similar analyses will be performed for:

- Lipid and lipoprotein parameters including low-density lipoprotein cholesterol (LDL-C), non-LDL-C, high-density lipoprotein cholesterol (HDL-C), non-HDL-C, total cholesterol, TG, apolipoprotein B (ApoB), and lipoprotein(a) (Lp[a]) particles, total Cholesterol:HDL ratio, LDL:HDL ratio (Note that the cholesterol and LDL to HDL ratios will be derived and do not come directly from the laboratory)
- NASH and fibrosis biomarkers including cytokeratin-18 (CK-18), fibrosis-4 (FIB-4), and enhanced liver function (ELF) or FIBROspect 2 or ProC3 test.
- Eicosanoids including 5-LOX-derived leukotriene B4 (LTB4), COX-derived prostaglandin E2 (PGE2), and 15-LOX-derived 15-hydroxyeicosatetraenoic acid (15-HETE) and lipoxin A4 (LXA4). For eicosanoids, descriptive statistics will be presented without any statistical testing.

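### A low-powered country-by-treatment test chooses the primary population in the protocol and still governs end-of-study pooling in the SAP; the analysis set should be fixed in advance and the two documents aligned

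*SAP*

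**What the plan says.** **Protocol.** Section 13.2.2 and the synopsis fit a country-by-treatment interaction for percent change in liver fat, 50 mg against pooled placebo. If p is at least 0.05, the primary analysis uses all US and China subjects. If p is below 0.05, "then the primary analysis will be conducted on subjects enrolled in the US and will maintain sufficient power".

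**SAP.** Section 3.5 takes a different position: "The primary analysis will not include any data from China, due to delays and uncertainty of enrollment in the Chinese cohort". Section 8.3.1.1 specifies the US-only model and section 9 records this as a change from the protocol. The interaction test stays in 8.3.1.2 for the end-of-study analysis: "A test for country-by-treatment interaction will be performed. If there is no interaction detected", the model is run "including all subjects from US and China (with no fixed effect for country"). If the interaction is significant, a separate China analysis is done, described as unpowered and supportive.

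**Carry-over to other endpoints.** SAP 8.3.2 says that at the end-of-study analysis a significant liver-fat interaction splits the 50 mg cohort by country for the key secondary endpoint and for ALT/AST and the endpoints analysed like them. Conversely, "if no country-by-treatment interaction is found in the primary efficacy endpoint, the interaction may be explored within the secondary endpoints".

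**Around the rule.** SAP 7.2 plans all analyses by country as well as overall. Neither document states the power of the interaction test or an acceptable size of country difference.

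**The concern.** A non-significant interaction shows only that the data could not separate the two effects. With 27 Chinese subjects split 18 to 9, that is the likely outcome even when the effects differ a great deal, so the rule would usually pool whatever the truth.

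Two things are at stake. Under the protocol, the population for the 50 mg test is chosen from the same outcome data that are then tested, while 13.2.2 says that the overall error rate is held at 0.05. Under the SAP, the test does not affect the primary analysis, but it decides which combined or separate analysis is run at the end of the study, and one endpoint's p-value sets the handling of others. SAP 8.3.1.1 also attaches the fixed-sequence error control to the final analysis, which is when the pretest operates.

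The documents also disagree about what is primary. The SAP is based on protocol version 6.0. The protocol text reviewed includes Cohort 3, which the SAP addendum ties to version 7.0, and it still carries the interaction rule for the primary analysis. The addendum covers Cohort 3 only and does not settle the matter.

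**Working it through.** **Inputs**
- SD: "it is conservatively assumed that the primary endpoint has a standard deviation of 30" (SAP 3.3).
- Effect: the stated power applies "if each mean treatment difference is at least 24" (SAP 3.3). No effect in China therefore means an interaction of 24 points.
- Level: "statistical inference will be based on 2-sided testing with a 5% significance level" (SAP 7).
- US: 30 on 50 mg, 30 pooled placebo (SAP 3.3). China: 18 and 9 (SAP 3.2). Total 87.

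**1. The plan's own power figures.** The plan states at least 80% for both dose comparisons, and at least 77% for 30 v 15. Simulating the two-sided Wilcoxon test on lognormal data (SD 30, difference 24, placebo mean 100 on a percent-of-baseline scale) gives 84% and 77%. The documents do not give the lognormal mean, so this is an assumption; normal data give 74–75% and 67%. The stated figures are reproducible for a plausible mean. No figure is stated for the interaction test.

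**2. Precision of the interaction.**
SE = 30 × √(1/30 + 1/30 + 1/18 + 1/9) = 30 × √0.2333 = 14.49.
With 87 − 6 = 81 df the t multiplier is 1.99, so the 95% half-width is 1.99 × 14.49 ≈ 29 points, wider than the planned effect of 24. For 80% power the true difference would have to be about 14.49 × (1.96 + 0.84) ≈ 41 points.

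**3. Chance of missing a real difference** (non-central t):

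| True effects (US v China) | SD 30 | SD 25 | SD 20 |
|---|---|---|---|
| 24 v 0 | 63% | 50% | 31% |
| 24 v 12 | 87% | 83% | 77% |

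Protocol 13.2.2 places the test in the 50 mg cohort. If that means only that cohort's 15 US placebo subjects, SE = 30 × √(1/30 + 1/15 + 1/18 + 1/9) = 15.49, and the miss rate for 24 v 0 at SD 30 is about 67%. A lognormal simulation gives about 61% with 30 US placebo subjects and 65–66% with 15.

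**4. What the pretest does to the 50 mg test.** Simulation at SD 30 with normal data, no covariates and equal placebo response in both countries. The procedure uses the pooled test if the interaction has p ≥ 0.05 and the US-only test otherwise.

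| True effects (US, China) | With pretest | US-only |
|---|---|---|
| 24, 24 | 95% | 86% |
| 24, 12 | 86% | 86% |
| 24, 0 | 74% | 86% |
| 0, 0 (type I error) | 5.8% | 5.0% |

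The excess error arises because, with no effect anywhere, the US-only test rejects about 21% of the time when the interaction happens to be significant: 0.05 × 0.21 + 0.95 × 0.05 ≈ 0.058.

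**5. Pooled estimate.** With China at zero the pooled difference averages (30 × 24 + 18 × 0)/48 = 15. The allocation also differs by country: China supplies 18/48 = 37.5% of the active group but 9/39 = 23% of placebo. With no country term, a country difference in placebo response would enter the pooled treatment effect.

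**The case against.** The case for leaving the plan alone has real substance.

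- **No claim of equivalence.** A reader might infer that p ≥ 0.05 is taken as proof that the two effects are the same. The documents do not say so. They speak only of an interaction not being detected.
- **China results will be visible.** A reader might also infer that a null result in China could be hidden by pooling. SAP 7.2 plans every analysis by country whatever the test shows, and 8.3.1.2 plans country subsets specifically to look at consistency.
- **The SAP's primary analysis is untouched.** It is US-only and section 9 records that as deliberate. The 2022 addendum says it is to be read with that SAP, so the SAP stayed in force. The pretest sits among the additional analyses.
- **The pretest can help.** It gains about 8 points of power when effects are equal and costs nothing when China has half the effect. The material loss needs no effect at all in China; at SD 20 even that case is about 97% v more than 99%.
- **The 63% is conditional.** It needs exactly zero effect in China and an SD that the plan calls conservative. Nothing in the documents suggests zero effect there. And 15 points is not bias if the target is the average effect in the enrolled mix; preferring the US effect is a choice.

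All of this stands as a limit on the point. It does not rescue the rule: the protocol still lets the test choose the primary population while claiming 0.05, the SAP still lets it choose the end-of-study analysis, and nothing says which result carries the conclusion if the pooled and by-country results disagree.

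**Conclusion.** The point holds in a limited form. The protocol and SAP conflict on whether the primary analysis is US-only or decided by an interaction test, and that test is too imprecise to be a pooling rule: a 95% CI of about ±29 points around a planned effect of 24. It misses the extreme case of 24 v 0 about 63% of the time, with a range from 31% (SD 20) to about 67% (SD 30 with 15 US placebo subjects). Where it selects the population, type I error is about 5.8% against a stated 5%. That inflation is small, but avoidable.

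These figures rest on full planned numbers. Fewer evaluable Chinese subjects, or more exclusions for extended dosing, would raise the miss rate. They do not show that the US and China effects differ, and they do not put the SAP's US-only primary result in doubt. The plan should be changed, but the issue is moderate.

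**What to change.** 1. In protocol 13.2.2 and the synopsis, state that the US-only analysis is primary whatever the interaction result, matching SAP 3.5.
2. In SAP 8.3.1.2 and 8.3.2, replace the p ≥ 0.05 / p < 0.05 rule with an end-of-study analysis set fixed in advance.
3. At the end-of-study analysis, always report the US effect, the China effect and their difference, each with a 95% CI. Label the combined US and China result supportive, and state that a non-significant interaction does not show consistency.
4. Do not let the liver-fat interaction p-value decide how the key secondary, ALT/AST or other endpoints are analysed.

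The cost is wording, since the by-country runs are already planned. The statistical price is that the combined result cannot become primary, which gives up about 8 points of power (95% v 86%) if the effects are truly equal. The SAP accepted that when it made the primary analysis US-only, and protocol 13.2.2 already regards the 90 US subjects as enough.
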